3.0 PROTOCOL SUMMARY

Sponsor	Merck & Co., Inc.
Protocol Title	A prospective digital quality improvement project to apply best clinical practices to patients at high risk of respiratory complications
Drugs	The following FDA cleared drugs will be used in this study: 
 • Sugammadex
Study Objectives	Primary Objective 
 1) Time to “fitness for discharge” from the recovery room, as noted by the time the anesthesiologist places the discharge order, before and after intervention.

	
2) Incidence of hypoxemia in the PACU before and after intervention as defined by documentation oxygen saturation below 90%
 
Secondary Objectives
 
 1) Performance of identified best practices before and after intervention. 2) Incidence of hypoxemia in the PACU before and after intervention as defined by documentation of oxygen saturation below 95% 3) The duration of supplemental oxygen needed by high risk patients before and after intervention 4) Postoperative reintubation rate 5) Unplanned upgrade of care (defined as patients who are sent to the ICU after being admitted to a regular ward)
Study Design	Historical prospective comparative effectiveness trial
Study Phases	
Retrospective Data Analysis
 
Perform a retrospective analysis on data contained in our data warehouse on the incidence of respiratory dysfunction in the post-operative care unit (PACU) before and after the introduction of sugammadex into clinical practice.
 
Respiratory depression pathway implementation
 
Develop and implement a clinical best practice pathway designed to prevent postoperative respiratory complications in higher risk patients (such as those with OSA or preexisting respiratory disease) using education and clinical decision support in patients.

Sample Size	~13,000 retrospective and ~6,500 prospective
Clinical Sites	Ronald Reagan UCLA Medical Center, UCLA Santa Monica Hospital
Study Population	RRUMC or UCLA Santa Monica patients aged 18 and older who had a general anesthetic with either rocuronium or vecuronium.
Inclusion Criteria	
One or more:
 
 • Obstructive or restrictive lung disease in EMR • OSA • Preoperative O2 sat <95% (avg/median of 12 hours before surgery) • BMI > 40 • Acute respiratory infection within 1 month prior to surgery

[figure not shown]

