25.0 POWER ANALYSIS AND SAMPLE SIZE DETERMINATION

25.1 Retrospective analysis

In order to assess the change in time to readiness for PACU discharge and postoperative respiratory dysfunction (duration of oxygen saturation below 90%) after the introduction of sugammadex we will construct two models. First, we will utilize propensity score matching (PSM)¹⁴ to adequately risk balance the patients pre/post sugammadex introduction (variables mentioned in section 2.4). We will use the nearest-neighbor PSM approach and start with a caliper of width equal to 0.2 of the standard deviation of the logit of the propensity score (as described by Austin¹⁵). We will assess balance of the covariates pre/post intervention by computing

standardized mean differences (SMD) for each variable and will use the rule of thumb “SMD less than 0.1”¹⁶ to indicate adequate balance. Finally, we will also construct a table of patient characteristics pre/post matching to see how well the algorithm balanced the patients. If individual covariates are not adequately balanced with the default propensity score matching algorithm, we will try different matching parameters until adequate balance is achieved (e.g. change the caliper size for what we consider a match and/or run a more advanced propensity score model including interaction or squared terms).

After adequate balance is observed, we will compare our outcomes of interest between pre/post periods using a linear (or log-linear) model for time to readiness and logistic regression for our binary outcome (postoperative respiratory dysfunction) using the propensity matched dataset. An interrupted time-series (also known as segmented regression) analysis as described by Wagner¹⁷ will be conducted for each outcome to estimate the pre-intervention time trend, immediate impact of intervention (change-point), as well as reliably estimating the slope change after the intervention. All estimates of interest from these models will be summarized with p-values and 95% confidence intervals.

Statistical analyses will be performed using R V3.5.1 (Vienna, AU) using the “*Match*” package for propensity score matching and p-values <0.025 (for our two primary outcomes) will be considered statistically significant utilizing the Bonferroni adjustment (0.05/2).

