25.2 Prospective analysis

The prospective analysis will largely follow a similar framework however we will focus on the primary and secondary outcomes as described above and will use a one year period prior to implementation as our baseline.

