At this point, we estimate that the pathway will recommend sugammadex for all patients in the medium or high-risk groups as well as some patients in the low risk group (i.e. those patients requiring deep neuromuscular blockade to facilitate surgical conditions such as robotic procedures, free flap cases and others). Given the large number of patients, Merck would supply one vial of study drug for each patient. Thus the total amount of study drug would be no more than 6,500 patients for the one year intervention time.

Given 1 year of data, we observed an overall average PACU discharge time of 152.54 minutes (SD=623.86). With one year of post-data, we are adequately powered (90%) to pick up a reduction in PACU discharge time as small as 27.04 (two-sample t-test, alpha=0.025). Since the current difference in PACU discharge time between low and high risk groups is 67.52 (subtracting 216.62-149.10, see table), we feel the 27.04 minimally detectable difference gives us a great chance of detecting a meaningful difference.

Given 1 year of data (pre-period), we observed the rate of patients with any time SpO2<90% was 4.6% (574/12,467). With one year of post-data, we are adequately powered (90%) to pick up a reduction in this rate if it decreases to around 3.7% in the post (chi-square test, alpha=0.025). Since the current difference in patients with any time with SpO2<90% between low and high risk patients is 5.2% (subtracting 9.2%-4.0%), we feel the minimally detectable difference of 3.7% (4.6%-3.8%) is feasible.

Table 2.

	suppl O2, mean (SD)	PACU disch. Time, mean (SD)	Reintubation, freq (%)	Unplanned upgrade, freq (%)	SpO2<90%, freq (%)	SpO2<95%, freq (%)
OVERALL(n=13,277)	74.81 (241.82)	152.54 (623.86)	89 (0.7%)	138 (1.0%)	574 (4.6%)	6510 (52.3%)
low (n=9,841)	74.48 (280.55)	149.10 (599.78)	63 (0.6%)	111 (1.1%)	372 (4.0%)	4603 (50.0%)
medium(n=2,997)	74.98 (95.67)	154.43 (536.58)	23 (0.8%)	22 (0.7%)	164 (5.8%)	1658 (58.8%)
high (n=439)	79.54 (88.44)	216.62 (1321.46)	3 (0.7%)	5 (1.1%)	38 (9.2%)	249 (60.9%)
Smallest detectable difference (90% power)	9.61	24.84	0.4%	0.4%	3.8%	50.3%

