- Preexisting respiratory disease: The presence of obstructive or restrictive lung disease as defined based on the structured data in the EMR such as previous PFT results, previous medication and previous diagnoses. For analysis purposes patients will be divided into low, medium and high risk groups based on the extent of their disease.

Statistical Methods:

All analysis will be performed by the study team at UCLA.

Retrospective analysis: In order to assess the change in time to readiness for PACU discharge and postoperative respiratory dysfunction (duration of oxygen saturation below 90%) after the introduction of sugammadex we will construct two models. First, we will utilize propensity score matching (PSM) to adequately risk balance the patients pre/post sugammadex introduction. We will use the nearest-neighbor PSM approach and start with a caliper of width equal to 0.2 of the standard deviation of the logit of the propensity score. We will assess balance of the covariates pre/post intervention by computing standardized mean differences (SMD) for each variable and will use the rule of thumb “SMD less than 0.1” to indicate adequate balance. Finally, we will also construct a table of patient characteristics pre/post matching to see how well the algorithm balanced the patients. After adequate balance is observed, we will compare our outcomes of interest between pre/post periods using a linear (or log-linear) model for time to readiness and logistic regression for our binary outcome (postoperative respiratory dysfunction) using the propensity matched dataset. An interrupted time-series (also known as segmented regression) analysis as described by Wagner will be conducted for each outcome to estimate the pre-intervention time trend, immediate impact of intervention (change-point), as well as reliably estimating the slope change after the intervention. All estimates of interest from these models will be summarized with p-values and 95% confidence intervals.

Statistical analyses will be performed using R V3.5.1 (Vienna, AU) using the “Match” package for propensity score matching and p-values <0.05 will be considered statistically significant.

Prospective analysis: The prospective analysis will largely follow a similar framework however we will focus on the primary and secondary outcomes as described above and will use a one year period prior to implementation as our baseline.

Power/Sample Size:

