Sugammadex was introduced into clinical practice at UCLA in May of 2016, thus we have well more than one year of data prior to and after sugammadex introduction. As a result, the power analysis and sample size discussion is roughly the same for the retrospective and prospective portions of this study.

Over the previous one year period, approximately 6,5000 patients received general anesthesia with the use of either rocuronium or vecuronium. Given that our surgical volumes are stable we would expect the sample size for the prospective portion of our study to be roughly the same. The table below contains the risk stratification for this group.

To determine the study power, we analyzed the incidence of the primary and secondary outcomes for our historical population. Because there is no current pathway, we are unable to explicitly model the power

for pathway compliance, however the power for the primary outcome as well as secondary outcomes were calculated.

In order to determine our power for the study variables patients were separated into low, medium, and high-risk groups. Low risk patients were those who had no prior documentation of OSA or respiratory disease prior to surgery. Medium risk patients were those with either OSA or respiratory disease and high risk patients were those with both diseases. It is important to note that this classification is significantly simplified as compared to the analysis that will be performed for either the retrospective or prospective studies as it fails to account for key factors such as severity of illness. Nonetheless we believe that these simplifications have the effect of underestimating the potential power and thus the below serves as a conservative estimate.

Given 1 year of data, we observed an overall average PACU discharge time of 152.54 minutes (SD=623.86). With one year of post-data, we are adequately powered (90%) to pick up a reduction in PACU discharge time as small as 24.84 (two-sample t-test, alpha=0.05). Since the current difference in PACU discharge time between low and high risk groups is 67.52 (subtracting 216.62

149.10, see table), we feel the 24.84 minimally detectable difference gives us a great chance of detecting a meaningful difference.

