Given 1 year of data (pre-period), we observed the rate of patients with any time SpO₂<90% was 4.6% (574/12,467). With one year of post-data, we are adequately powered (90%) to pick up a reduction in this rate if it decreases to around 3.8% in the post (chi-square test, alpha=0.05). Since the current difference in patients with any time with SpO₂<90% between low and high risk patients is 5.2% (subtracting 9.2%-4.0%), we feel the minimally detectable difference of 0.8% (4.6%-3.8%) is feasible.

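### The 90% power figures assume about 13,277 patients per period, yet the plan also gives about 6,500 prospective patients, and the PACU-time benchmark comes from a different population

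*Combined protocol and SAP*

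**What the plan says.** **Power.** Section 26.0 takes a one-year mean PACU discharge time of 152.54 minutes (SD 623.86). It gives a 90%-power detectable reduction of 27.04 minutes from a two-sample t-test at alpha 0.025. The SAP (Power/Sample Size) gives 24.84 minutes at alpha 0.05. For SpO2<90%, the baseline is 574/12,467 = 4.6%, with a detectable post-period rate of about 3.7% (section 26.0) or 3.8% (SAP). Both documents present the power discussion as essentially common to the two portions of the study.

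**Prospective numbers.** These do not agree:
- Protocol Summary (3.0): "13,000 retrospective and ~6,500 prospective".
- Section 7.0: an anticipated sample size of 6,500.
- Section 13.0: a patient is enrolled once eligible and supplied with study drug.
- Section 29.4.3: administration of study drug is a criterion for inclusion.
- Section 26.0: about 13,000 patients in the past year, with a similar number expected prospectively. It presents 6,500 as an upper limit on drug supply.
- SAP, Power/Sample Size: the one-year count is printed as 6,5000.

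**Benchmark.** Section 26.0 argues: "Since the current difference in PACU discharge time between low and high risk groups is 67.52". The SAP concludes: "we feel the 24.84 minimally detectable difference gives us a great chance of detecting a meaningful difference". For desaturation, the SAP sets a 5.2-point contrast between high- and low-risk patients beside its detectable drop and says "we feel the minimally detectable difference of 0.8% (4.6%-3.8%) is feasible".

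**Model.** Section 25.1 compares matched periods "using a linear (or log-linear) model for time to readiness". The SAP (Statistical Methods) does the same, "using a linear (or log-linear) model for time to readiness and logistic regression for our binary outcome". Both also plan an interrupted time series for each outcome. Section 25.2 adds: "The prospective analysis will largely follow a similar framework".

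**The concern.** A power statement holds only for the number of patients who enter the comparison. If the prospective comparison uses patients who received study drug, it has about half the number behind the stated figures. The detectable differences would then be larger than stated, and the power for the stated differences well below 90%.

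The PACU-time reassurance has a separate problem. The detectable difference is a pre/post shift in the mean of the whole cohort. The 67.52 minutes is a cross-sectional gap between a small high-risk group and the low-risk group. The second being larger than the first says little about whether the pathway can move the cohort mean by the detectable amount. A reader of section 26.0 would take more comfort from the comparison than it can give.

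**Working it through.** **Inputs.** SD 623.86, mean 152.54, overall n = 13,277, and risk-group means, SDs and counts (section 26.0, Table 2). SpO2<90% rate 574/12,467 = 4.604% (section 26.0). Prospective n of about 6,500 (sections 3.0 and 7.0). Tests are taken as two-sided, which is the version that reproduces the stated figures.

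**Reproducing the plan's PACU figures.** Detectable difference = (z for alpha/2 + 1.2816) × SD × √(1/n1 + 1/n2).
- 13,277 per period: standard error = 623.86 × √(2/13,277) = 7.657.
- Alpha 0.025: (2.2414 + 1.2816) × 7.657 = 26.97 minutes (stated 27.04).
- Alpha 0.05: (1.9600 + 1.2816) × 7.657 = 24.82 minutes (stated 24.84).

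The arithmetic is sound, and it requires about 13,277 patients in each period.

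**Reproducing the SpO2<90% figures.** With 12,467 per period (the stated denominator), the 90%-power post-period rate is 3.71% at alpha 0.025 and 3.78% at alpha 0.05. These match the stated 3.7% and 3.8%. Power for 3.7% at alpha 0.025 is 91%.

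**With about 6,500 prospective patients, same SD and baseline rate.** The last column is power to detect 27.04 minutes.

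| Comparison | Detectable, alpha 0.025 | Detectable, alpha 0.05 | Power, alpha 0.025 |
|---|---|---|---|
| 13,277 v 13,277 | 26.97 min | 24.82 min | 90% |
| 13,277 v 6,500 (unmatched) | 33.27 min | 30.61 min | 73% |
| 6,500 v 6,500 (e.g. 1:1 matched) | 38.55 min | 35.47 min | 59% |

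For example, at 6,500 per period the standard error is 623.86 × √(2/6,500) = 10.943, and 3.523 × 10.943 = 38.55. Power for 27.04 is Φ(27.04/10.943 − 2.2414) = Φ(0.230) = 59%.

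For SpO2<90% at 6,500 per period and alpha 0.025, the detectable rate is 3.39%, a drop of 1.2 points. Power for 3.7% is 63%.

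**The 67.52-minute benchmark.**
- Contrast: 216.62 − 149.10 = 67.52, from 439 high-risk and 9,841 low-risk patients. The high-risk group is 439/13,277 = 3.3% of the cohort.
- Standard error: √(1321.46²/439 + 599.78²/9,841) = 63.36. The 95% CI is 67.52 ± 1.96 × 63.36, or about −57 to 192.
- One scenario: bringing every high-risk patient to the low-risk mean lowers the cohort mean by 67.52 × 439/13,277 = 2.2 minutes, against a detectable 27.04.
- SpO2<90%, same scenario: the high-risk denominator is back-calculated as 38/0.092 = 413. Then 38 − 413 × 0.04 = 21.5 fewer events, and 21.5/12,467 = 0.17 points, against a detectable drop of 0.8 to 0.9 points.

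**The case against.** The strongest reply is that 6,500 may not be the analysis set at all. Section 26.0 expects prospective volume to match the historical 13,000 and introduces 6,500 as a ceiling on drug supply. On that reading the stated power stands. This is a fair limit: the documents do not settle the matter. But sections 3.0 and 7.0 give 6,500 as the sample size, and sections 13.0 and 29.4.3 tie enrolment or inclusion to the drug, so the conflict is real. A reader might infer that the trial is underpowered or that the calculation is wrong. The documents support neither claim; the calculation is right for the n it uses.

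The 13,277-versus-6,500 case also fits the planned matched analysis poorly, since it sets an unmatched baseline against a selected group. It is shown only as an intermediate case. The matching ratio is not stated, so 6,500 pairs is itself an assumption.

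On the benchmark, 67.52 minutes may be meant as a yardstick for clinical importance and not as a forecast. Even so, it is not in the same population as the detectable difference, and it is imprecise. The reply does hold against one further inference, that 2.2 minutes caps what the pathway could achieve. Eligibility is much wider than the high-risk class, some low-risk patients would also be covered, and section 26.0 calls the classes simplified.

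On the model, a reader might infer that the team will run linear and log-linear analyses and report the better one. Nothing says both will be run. The endpoint is defined in minutes, the power is for raw minutes, and linear is named first. The wording also sits in the retrospective section and reaches the prospective part only by reference. It is missing detail, not an error, and either model would be acceptable.

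**Conclusion.** The power statement does not hold for the prospective portion under every number the plan gives. It is correct for about 13,277 patients per period (12,467 for SpO2<90%). At 6,500 per period and alpha 0.025, the detectable PACU-time difference rises by more than 40% (38.55/26.97 = 1.43) and power for the protocol's own 27.04 minutes is 59%. For SpO2<90%, power for 3.7% falls from 91% to 63%. These results assume an unchanged SD and baseline rate and no gain from covariate adjustment or matching. They are conditional on 6,500 being the analysed number, which the plan must decide.

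The PACU-time benchmark is mismatched whichever n applies. The SpO2<90% argument has the same fault in milder form, since it claims only feasibility.

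The open choice of model is secondary. It matters here because, if a log-scale model is chosen, no stated detectable effect applies to it.

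**What to change.** - Reconcile sections 3.0, 7.0, 13.0, 26.0 and 29.4.3 and the SAP on who is in the prospective analysis. State that set and its expected n in each period, after matching if matching is used.
- Restate the detectable PACU-time and SpO2<90% differences for that set at the plan's alpha, separately from the retrospective portion, in section 26.0, Table 2 and the SAP.
- Delete the 67.52-minute argument, or replace it with an expected pre/post effect in the population to which the detectable difference applies. Treat the 5.2-point SpO2<90% argument in the same way. Label any gap-closure figure as one scenario.
- While restating, name one primary model and effect measure for PACU time, give its rank against the interrupted time series, and express the detectable effect on that scale. A geometric mean ratio applies only if log-linear means a log-transformed outcome; a log-link model targets a ratio of arithmetic means. The log-scale SD is not in the documents and would have to come from the historical data already held.

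The cost is wording plus one recalculation on existing data, with no added enrolment or drug supply. The drawback is that the restated figures will look less favourable if the smaller set is chosen, and the feasibility text loses its most reassuring sentence.

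### No deciding test is named for either primary outcome, the protocol and SAP thresholds conflict (0.025 and 0.05), and the 27.04-minute detectable difference does not apply to the segmented regression

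*Combined protocol and SAP*

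**What the plan says.** Protocol 25.1 first plans a matched comparison: "we will compare our outcomes of interest between pre/post periods using a linear (or log-linear) model for time to readiness and logistic regression" for the binary outcome. It then adds a second analysis: "An interrupted time-series (also known as segmented regression) analysis", which "will be conducted for each outcome to estimate the pre-intervention time trend, immediate impact of intervention (change-point"), together with the change in slope. Reporting covers both models: "All estimates of interest from these models will be summarized with p-values and 95% confidence intervals". The decision threshold is "p-values <0.025 (for our two primary outcomes) will be considered statistically significant utilizing the Bonferroni adjustment (0.05/2").

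The SAP (Statistical Methods) repeats both analyses, but there "p-values <0.05 will be considered statistically significant", with no adjustment. Protocol 25.2 and the matching SAP paragraph carry a similar framework into the prospective phase, with a one-year baseline, and add no deciding test.

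Power is given only for simple two-group tests. Section 26.0 states 90% power for 27.04 minutes ("two-sample t-test, alpha=0.025") and for a fall in SpO2<90% from 4.6% to 3.7% (chi-square, 0.025). The SAP gives 24.84 minutes and 3.8% at 0.05. The last row of Table 2 in section 26.0 also shows 24.84 and 3.8%, which are the 0.05 figures.

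**The concern.** Each outcome gets three p-values that bear on the intervention: the matched period term, the level change and the slope change. The pre-intervention trend is not an effect test. The divisor of 2 counts outcomes and leaves out the number of tests per outcome. Because no term is designated, the choice of which result to present as the primary finding can be made after the data are seen.

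That matters more here than in a randomised trial. In a before/after design with any underlying trend, the matched regression and the segmented regression can disagree.

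Two further gaps follow. The documents give two thresholds for the same analysis, and 95% intervals match neither the protocol's threshold nor its Bonferroni logic: a result with p = 0.03 would have an interval excluding no effect and still be declared non-significant. And the reader cannot tell to which planned test the 90% power applies.

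**Working it through.** **Inputs.** SD of PACU discharge time 623.86 minutes (26.0); 13,277 patients in the historical year (Table 2), with the post period taken as equal because 26.0 expects stable volume; SpO2<90% rate 574/12,467 (26.0); thresholds 0.025 (25.1) and 0.05 (SAP); 90% power. Sidedness is not stated; two-sided reproduces the figures.

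**Step 1: reproduce the stated power.** The standard error of a simple pre/post difference is 623.86 × √(2/13,277) = 7.66 minutes.
- At 0.025: (2.241 + 1.282) × 7.66 = 26.97 minutes, against 27.04 stated. Power at 27.04 is 90.1%.
- At 0.05: 24.82 minutes, against 24.84 in the SAP. Power at 24.84 is 90.0%.
- SpO2<90%, 4.6% to 3.7%, with 12,467 per period at 0.025: 90.9%.

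So the plan's figures are correct for an unmatched comparison using every patient.

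**Step 2: precision of the segmented terms.** Assume one year each side, even accrual, no autocorrelation and no matching. Within a period of unit length, time has variance 1/12, so the fitted value at the break has variance (σ²/n) × (1 + 0.5² ÷ 1/12) = 4σ²/n. The level change therefore has twice the standard error of the simple difference: 2 × 7.66 = 15.31 minutes.
- Detectable level change at 0.025 and 90% power: (2.241 + 1.282) × 15.31 = 53.9 minutes.
- Power for a level change of 27.04 minutes: Φ(27.04/15.31 − 2.241) = 31.7%.
- Power of the level term for SpO2 4.6% to 3.7%: about 33%.

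**Step 3: error rate if any effect term may be claimed.** In this layout the pre/post difference and the level change correlate at 0.5, and the slope change is uncorrelated with both. Simulating three test statistics with these correlations (2,000,000 draws) gives:

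| Rule | One outcome | Two independent outcomes |
|---|---|---|
| Three terms, each at 0.025 | 7.0% | 1 − (1 − 0.0702)² = 13.6% |
| Same, if all terms were independent | 7.3% | 1 − 0.975⁶ = 14.1% |
| Bonferroni bound | 3 × 0.025 = 7.5% | 6 × 0.025 = 15% |
| One named term at 0.025 | 2.5% | 1 − 0.975² = 4.9% |
| One named term at the SAP's 0.05 | 5% | 1 − 0.95² = 9.75% |

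**Step 4: what a pre/post deciding test leaves open.** Suppose discharge time drifts by 1 minute per month with no intervention effect (an assumption). Over 12 + 12 months the period means then differ by 12 minutes, and the pre/post test at 0.025 rejects with probability Φ(12/7.66 − 2.241), about 25%. At 0.5 minutes per month it is about 7%.

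**The case against.** The strongest reply is that the inflation is conditional. No section says that significance on any one term counts as success. 25.1 uses the matched regression to compare the periods and the segmented regression to estimate quantities, and only a pre/post comparison is powered, so the segmented regression may have been meant as estimation. That reading is plausible, and for this reason the error rates above are stated with an if. It does not close the gap: p-values attach to estimates from both models, one threshold is stated for all of them, and nothing calls the segmented terms supportive.

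Second, the 13.6% needs two primary outcomes. The Study Endpoints list, section 10.0 and the SAP label only PACU discharge time as primary, whereas the Protocol Summary objectives and 25.1 treat two outcomes as primary. With one, the figure is 7.0%. Positive correlation between the outcomes also lowers it: to about 12.8% at a correlation of 0.5 and 11.9% at 0.7 (assumed values).

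Third, 12 + 12 months is an assumption for the retrospective analysis. A one-year baseline is set only for the prospective phase, and 26.0 says more data exist on both sides of sugammadex introduction.

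Fourth, choosing the matched period term as decisive would demote the only planned analysis that models secular trend. Step 4 shows that this is a real cost.

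A 95% interval beside a 0.025 threshold is a reporting mismatch and does not alter the decision rule.

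**Conclusion.** The gap in pre-specification stands. As written, the alpha rule does not secure 5%, because it fixes neither the deciding coefficient nor, across the two documents, the threshold. If any effect term may be claimed at 0.025, the error rate is about 7.0% for one primary outcome and up to about 13.6% for two (bound 15%), given 12 + 12 months, no autocorrelation and independent outcomes. At the SAP's 0.05 it is 9.75% for two outcomes even with one test each. The 27.04 minutes is sound for an unmatched t-test on about 13,277 per period, is an approximation for the matched regression, and does not apply to the level change, where about 54 minutes is the comparable figure.

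Some stronger readings are tempting but not supported:
- A reader might take an error rate of about 25% from applying six tests at the SAP's 0.05. That mixes the multiplicity question with the separate threshold conflict, and the SAP claims no 5% family-wise rate.
- A reader might quote 77 minutes for the level change, from 6,500 patients in both periods (2 × 38.55). The Protocol Summary gives about 13,000 retrospective and 6,500 prospective; with 13,277 and 6,500 the same method gives 2 × 33.27, about 67 minutes. Part of that rise reflects sample size, and the model choice alone accounts for the factor of 2.
- A reader might say the stated power covers exactly one planned test. It covers none exactly: matching can drop patients, and the discharge-time model may be log-linear.
- A reader might conclude that the matched regression must be the deciding test. The documents do not settle this; what is needed is that one test be named.

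**What to change.** In 25.1, 25.2 and the SAP:

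1. Name one deciding coefficient for each primary outcome, tested at two-sided 0.025 and reported with a 97.5% interval. State whether SpO2<90% is a second primary outcome, since the divisor of 2 presumes it.
2. Replace the SAP's 0.05 with 0.025, and bring the SAP power text and the last row of Table 2 into line.
3. Label the remaining effect terms supportive, reported with intervals and without a significance claim.
4. Say which test the detectable difference describes. If it is the matched period term, state that 27.04 minutes assumes no loss of patients in matching, and that the segmented regression will be reported alongside as the check for secular trend. If it is the segmented level term, restate the figure: about 54 minutes at 13,277 per period under the assumptions above.

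The cost is a few sentences and no new data. The test not chosen can no longer carry a significance claim, and a pre/post deciding test remains exposed to secular trend. If the team prefers that all six terms keep a claim, dividing 0.05 by six (0.0083) is the alternative; the pre/post detectable difference then rises to 30.01 minutes and power at 27.04 falls to 81.4%.
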